3.3.1. Additional Patient-Reported Outcomes (PRO)

- Response based on NRS4 for severity at Week 8;
- Time to achieve a ≥ 4 -point improvement in the numerical rating scale (NRS) for severity of pruritus from baseline;
- Response based on achieving ≥ 1 (clinically important response or CIR) point improvement from baseline in the total PSAAD score at all scheduled time points;
- Change from baseline in PSAAD score at all scheduled time points except Week 12;
- Change from baseline in DLQI / CDLQI at all scheduled time points;
- Response based on achieving a DLQI / CDLQI score < 2 (Basra et al. 2015) at all scheduled time points (among adult / adolescent subjects with a score ≥ 2 at baseline);

- Response based on achieving ≥ 4 -point improvement from baseline (Basra et al. 2015) in the DLQI score at all scheduled time points (among adult subjects with a score ≥ 4 at baseline);
- Response based on achieving ≥ 2.5 -point improvement from baseline in the CDLQI score at all scheduled time points (among adolescent subjects with a score ≥ 2.5 at baseline);
- Change from baseline in each component (anxiety and depression) of the HADS score at all scheduled time points;
- Response based on achieving a score < 8 in each component (anxiety and depression) of the HADS score (Zigmond and Snaith, 1983) at all scheduled time points (among adult subjects with a score ≥ 8 at baseline);
- Response based on achieving a score < 11 in each component (anxiety and depression) of the HADS score (Zigmond and Snaith, 1983) at all scheduled time points (among adult subjects with a score ≥ 11 at baseline);
- Change from baseline in POEM at all scheduled time points;
- Change from baseline in PtGA at all scheduled time points;
- Response based on PtGA score of clear (0) or almost clear (1); and a reduction from baseline of ≥ 2 points at all scheduled time points (among subjects with a score ≥ 2 at baseline);
- Change from baseline in EQ-5D-5L / EQ-5D-Y at all scheduled time points;
- Change from baseline in FACIT-F / Peds-FACIT-F at Week 12;
- Change from baseline in physical and mental component scores of SF-36v2, acute at Week 12.

3.3.2. PK Endpoints

The PK endpoints and the analysis methods for these endpoints are described in a separate analysis plan.

3.4. Baseline Variables

In general, for all analyses, baseline will be defined based on observations collected prior to first dose. Baseline values for demographics, medical and other history, atopic dermatitis history will be based on measures collected at Visit 1 / Screening visit. Study Day 1 is defined as the day the subject receives first dose of study drug. For purposes of all other analyses including analyses for change from baseline, the baseline value will be defined as measured on Day 1 (before time of first dose, if time is available). If a value is missing on Day 1, then the last available observation before Day 1 will be used. For the PSAAD score,

baseline will be defined as the average of all values recorded from Day -6 until Visit 2 / Day 1. For analysis purposes, randomization strata information will be taken from the Case Report Form (CRF).

3.5. Safety Endpoints

Safety will be assessed by the spontaneous reporting of AEs, physical examinations, and clinical laboratory results in all subjects who receive at least one dose of the investigational product. Unscheduled safety assessments may be performed at any time during the study to assess any perceived safety concerns. Endpoints will be assessed as:

- Incidence of treatment emergent adverse events.
- Incidence of SAEs and AEs leading to discontinuation.
- Incidence of clinical abnormalities and change from baseline in selected clinical laboratory values, ECG measurements, and vital signs.

The safety endpoints will be defined in accordance with Clinical Data Interchange Standards Consortium (CDISC) aligned Pfizer Standards (CaPS).

3.5.1. Adverse Events

An adverse event will be considered a Treatment-Emergent Adverse Event (TEAE) if the event started during the effective duration of treatment. All events that start on or after the first dosing day and time / start time, if collected, but before the last dose plus the lag time (28 days) will be flagged as TEAEs. The algorithm will not consider any events that started prior to the first dose date.

A 3-tier approach will be used to summarize AEs. Under this approach, AEs are classified into one of 3 tiers. Different analyses will be performed for different tiers (See [Section 6.9.1](#)).

Tier-1 events: These are pre-specified events of clinical importance and are maintained in a list in the product's Safety Review Plan. Herpes zoster and serious infections have been identified as Tier-1 events. No other Tier-1 events have been identified so far and the study team will continue monitoring all safety events.

Tier-2 events: These are events that are not Tier-1 but are "common". A MedDRA Preferred Term (PT) is defined as a Tier-2 event if there are at least 4 subjects with an event in any treatment group.

Tier-3 events: These are events that are neither Tier-1 nor Tier-2 events.

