Subjects who have chronic moderate to severe AD as defined per the inclusion criteria will be randomized to receive 200 mg or 100 mg PF-04965842 once daily (QD), or matching placebo. Investigators, subjects, and the sponsor study team will be blinded as to treatment group.

After providing informed consent, subjects will be assessed for study eligibility at the screening visit. For subjects younger than 18 years old (or country-specific age of majority), their parent(s)/legal guardian will provide supplementary or sole written consent and minor children will provide assent, according to local regulations and rules regarding ability to give assent and consent. Subjects will undergo screening within 28 days prior to randomization. During the screening period, treatments for AD will be washed out, as applicable, according to eligibility requirements. Subjects may be re-screened once if they fail the screening evaluation for reasons related to incidental transitory conditions, unless the reason for the screen failure is the disease severity inclusion criteria.

Subjects who continue to meet eligibility criteria at baseline will undergo Day 1/baseline assessments and be randomized in a 2:2:1 ratio to receive 200 mg PF-04965842 (N=150) or 100 mg PF-04965842 QD (N=150) or matching placebo (N=75) from Day 1.

Randomization will be stratified by baseline disease severity (moderate [IGA = 3] vs. severe [IGA = 4] AD), and, age <18 and ≥18. Eligible subjects must have a documented history of inadequate response or intolerance to treatment with topical AD medications or have required systemic therapies for control of their disease.

Study Treatments

- Doses of PF-04965842 will be 200 mg or 100 mg taken QD orally, or matching placebo.
- Treatment duration will be 12 weeks (randomized period).
- Subjects who do not enroll into the long term extension study, B7451015, will enter a 4 week follow-up post treatment period.

Statistical Methods

A total sample of 375 subjects, with 150 on PF-04965842 200 mg QD, 150 on PF-04965842 100 mg QD and 75 on placebo (2:2:1 randomization) would provide at least 95% power to detect a difference of at least 20% in IGA response rate between PF-04965842 200 mg QD (or PF-04965842 100 mg QD) and placebo, assuming the placebo response rate is 6% at Week 12.

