- l. A documented TB test performed within 12 weeks prior to Day 1 is acceptable. Subjects with a history of tuberculosis may not require TB testing as per the protocol exclusion criteria in [Section 4.2](#). Perform TB test procedure using the QuantiFERON[®]-TB Gold In Tube Test (or Purified Protein Derivative). A negative PPD test can be substituted for the QuantiFERON[®]-TB Gold In-Tube test only if the central laboratory is unable to perform the QuantiFERON[®]-TB Gold In-Tube test or cannot determine the results to be positive or negative and the Pfizer Medical Monitor approves it on a case-by-case basis. In addition to protocol required TB testing, sites should follow their local standards for TB status determination, which may include chest X-ray. See [Section 7.2.3](#).
- m. A pharmacokinetic (PK) blood sample will be collected prior to dosing at the study site on Week 4.

- n. PK blood samples will be collected at 0.5 hours (± 15 min) postdose at the Week 4 visit and at 0.5 hours (± 15 min) and 4.0 hours (± 30 min) postdose at the Week 12 visit (EOT/ET). For ET visits, if the subject discontinues before Week 4 do not collect PK samples. If the ET visit occurs after Week 4, collect PK samples only if the subject takes the investigational product at the site visit.
- o. Subjects should take the medication from study Days 1 to 85. Subjects will be encouraged to take the medication in the morning whenever possible; however, at study visit days, subjects are to be instructed to refrain from dosing at home, and are to take the dose in the clinic.
- p. Site staff is to administer the C-SSRS, SBQ-R and PHQ-8 to all subjects at screening and score immediately. Subjects who have recent or active suicidal ideation or behavior or clinically significant depression will be excluded from the study or discontinued from the study per [Section 4.2](#), [Section 7.4.1](#), [Section 7.4.2](#) and [Section 7.4.3](#). For subjects meeting exclusionary results on the C-SSRS, SBQ-R and PHQ-8, it is recommended the subject's primary care physician (PCP) should be informed, and the subject referred to a mental health professional, either by the PCP or the investigator according to their usual practice.

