8.1.4. Time Period for Collecting AE/SAE Information

The time period for actively eliciting and collecting AEs and SAEs (“active collection period”) for each subject begins from the time the subject/parent(s)/legal guardian, if applicable, provides informed consent, which is obtained before the subject’s participation in the study (ie, before undergoing any study-related procedure and/or receiving investigational product), through and including a minimum of 28 calendar days; except as indicated below after the last administration of the investigational product.

For subjects who are screen failures, the active collection period ends when screen failure status is determined.

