8.1.4.2. Recording Non-serious AEs and SAEs on the CRF

During the active collection period, both non-serious AEs and SAEs are recorded on the CRF.

Follow-up by the investigator may be required until the event or its sequelae resolve or stabilize at a level acceptable to the investigator, and Pfizer concurs with that assessment.

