2.2. Study Design

This is a randomized, double-blind, placebo-controlled, parallel-group, Phase 3 study to evaluate the efficacy and safety of PF-04965842 monotherapy in subjects aged 12 years and older with moderate to severe AD and a body weight ≥ 40 kg. The treatment duration is 12 weeks. Subjects will be screened within 28 days prior to the first dose of investigational product to confirm that they meet the subject selection criteria for the study. A total of approximately 375 subjects will be enrolled from approximately 75 sites located globally. A study design schematic is presented in Figure 1.

Figure 1 Study Design Schematic

* At Week 12, eligible subjects may enter a long-term extension study; all other subjects enter the 4 week follow-up period

Qualified subjects completing the 12-week treatment period of the study will have the option to enter a long-term extension (LTE) study B7451015. Subjects discontinuing early from treatment, or who are otherwise ineligible for the LTE study, will undergo a 4-week follow-up period in B7451012.

Subjects who have chronic moderate to severe AD as defined per the inclusion criteria and have a documented history of inadequate response or intolerance to treatment with topical AD medications will be randomized in a 2:2:1 ratio to receive 200 mg PF-04965842 (N=150) or 100 mg PF-04965842 QD (N=150), or matching placebo (N=75) from Day 1. Randomization will be stratified by baseline disease severity (moderate [IGA=3] and severe [IGA=4] AD) and age (age < 18 and ≥ 18 years). Investigators, subjects, and the sponsor study team will be blinded as to treatment group.

A full schedule of activities for the study is provided in [Appendix 9](#).

Study Treatments

- Doses of PF-04965842 will be 200 mg or 100 mg taken QD orally, or matching placebo;

- Treatment duration will be 12 weeks;

Sample Size Determination

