5.2.6. Analyses of Tier-1 and Tier-2 Events

Number and percentage of subjects with AEs over the duration of treatment will be provided for each treatment group. Tier-1 and Tier-2 events will be analyzed using methods proposed by Chan and Zhang (1999). Exact methods will be used for Tier-1 events while an asymptotic method will be used for Tier-2 events. Risk differences (each PF-04965842 dose group compared to placebo) and 2-sided 95% CIs will be reported. P-values will be reported only for Tier-1 events.

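### The treatment-emergent window runs to last dose plus 28 days and does not stop when a subject enters the extension study, so extension-period events can be credited to the randomised arm, including placebo

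*SAP*

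**What the plan says.** - **Window.** SAP 3.5.1 starts the window at the first dose ("The algorithm will not consider any events that started prior to the first dose date"). Later events are counted if they start at or after that dose "but before the last dose plus the lag time (28 days) will be flagged as TEAEs". No other stopping rule is given.
- **Collection.** Protocol 8.1.4 runs active collection from consent "through and including a minimum of 28 calendar days; except as indicated below after the last administration of the investigational product". The only exception that follows is for screen failures. Protocol 8.1.4.2 adds: "During the active collection period, both non-serious AEs and SAEs are recorded on the CRF".
- **Rollover.** The footnote to the design figure in SAP 2.2 reads: "At Week 12, eligible subjects may enter a long-term extension study; all other subjects enter the 4 week follow-up period". The Study Treatments part of the Protocol Summary says the same from the other side: "Subjects who do not enroll into the long term extension study, B7451015, will enter a 4 week follow-up post treatment period". Eligibility for rollover is not limited by arm. Under Protocol 6.2.7, only completers who do not roll over go on to Visit 9.
- **Dosing period.** Schedule of Activities, footnote o: "Subjects should take the medication from study Days 1 to 85".
- **Use.** SAP 4.3 classifies subjects by the study treatment they actually received and has no censoring at rollover. SAP 5.2.6 and 6.9.1 compare each dose with placebo by risk differences with 95% confidence intervals. P-values are added for the Tier-1 events, herpes zoster and serious infections.

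**The concern.** For a completer who rolls over, the 28 days after the last dose are not an untreated follow-up period. They are the first weeks of another study. Read literally, the rule assigns events from those weeks to the arm of this study. If extension drug is active and raises event risk, former placebo subjects bring on-drug events into the placebo column and the drug-placebo difference shrinks.

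If post-rollover events never reach this study's database, a different problem arises. The lag is then observed for subjects who do not roll over and missing for those who do. Length of follow-up would depend on a choice made after randomisation, and that choice may differ by arm. Either way, the comparative adverse event tables rest on a window that the SAP has not fully defined.

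**Working it through.** The plan gives no figure on this point to reproduce. The check is window arithmetic followed by a conditional illustration.

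**1. Overlap.** A last dose on Day 85 (Schedule of Activities) plus 28 is Day 113. Events must start before that, so the window is Days 1-112, of which 112 − 85 = 27 days follow the last dose (27/112 = 24%). If a share r of an arm rolls over with a gap of g days to the first extension dose, the share of the arm's window spent on extension drug is r × (27 − g)/112:

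| Rollover r (assumed) | g = 0 | g = 14 days |
|---|---|---|
| 50% | 12% | 6% |
| 70% | 17% | 8% |
| 90% | 22% | 10% |
| 100% | 24% | 12% |

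**2. Common event.** Assumptions: extension drug is active, hazards are constant, true incidence by Day 85 is 40% on placebo and 60% on active, and each arm would otherwise keep its in-trial hazard through the lag.

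- Hazards per day: −ln(0.60)/85 = 0.00601 for placebo and −ln(0.40)/85 = 0.01078 for active.
- Uncontaminated 112-day window: placebo 1 − exp(−112 × 0.00601) = 49.0%, active 1 − exp(−112 × 0.01078) = 70.1%, difference 21.1 points.
- Placebo subject who rolls over with no gap: 1 − exp(−85 × 0.00601 − 27 × 0.01078) = 55.2%.
- Placebo arm at 70% rollover: 0.7 × 55.2 + 0.3 × 49.0 = 53.3%, difference 16.8 points. At 90%: 54.5%, difference 15.6 points.
- With a 14-day gap, a rollover placebo subject has 99 days at the placebo hazard and 13 at the active hazard, giving 52.1%. The arm becomes 51.1-51.7% and the difference 19.0-18.4 points.

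Most of the rise from 40% is simply longer follow-up, since 49.0% is reached with no extension drug at all. The part due to extension drug, with no gap, is about 4 to 6 points.

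**3. Rare event.** Same assumptions, with 0.5% versus 2.0% by Day 85, scaled linearly.

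- Uncontaminated: 0.5 × 112/85 = 0.66% and 2.0 × 112/85 = 2.64%, difference 1.98 points.
- Contaminated placebo: 0.5 + (27/85) × [2.0r + 0.5(1 − r)] = 0.99% at 70% and 1.09% at 90% rollover. The differences are 1.64 and 1.55 points.
- In subjects, the excess on placebo is 75 × (0.99 − 0.66)% = 0.25 at 70% and 75 × (1.09 − 0.66)% = 0.32 at 90%.

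**4. Events held only in the extension database.** The lag is now seen only in non-rollovers. With the common-event figures, each arm's rate is r × (Day-85 rate) + (1 − r) × (112-day rate):

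| Rollover, placebo / active (assumed) | Placebo | Active | Difference |
|---|---|---|---|
| 80% / 80% | 41.8% | 62.0% | 20.2 points |
| 70% / 90% | 42.7% | 61.0% | 18.3 points |
| 90% / 70% | 40.9% | 63.0% | 22.1 points |

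In this case the direction depends on which arm rolls over more.

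**The case against.** The strongest reply is that contamination of placebo needs three things the documents do not state: active drug for former placebo subjects in B7451015, a first extension dose within the 28 days, and entry of those events in this study's database. The third is in real doubt. SAP Section 2 covers data collected in B7451012, B7451015 is a separate study, and rollover subjects have no scheduled visit here after Week 12. This stands. It makes the size and direction conditional, but it does not supply the missing rule, and Protocol 8.1.4 on its face keeps collection open here.

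A second reply is that SAP 3.5 defers to the sponsor's CaPS standard, which might truncate at rollover. That cannot be checked from the documents. The SAP's version history says the 3.5.1 definition was itself updated to match the CaPS algorithm, so the visible rule is the best evidence of what will be programmed, and it has no truncation.

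A reader might infer that the plan is shown to bias the safety comparison towards no harm. The documents do not support that. It follows only if events are captured here and extension drug raises risk. For the rare event, the contaminated difference (1.55 to 1.64 points) is not below the on-treatment difference of 2.0 − 0.5 = 1.5 points. It is smaller only against a clean window of equal length.

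A reader might also infer that SAP 5.2.6 sets a second, conflicting window, since it says "Number and percentage of subjects with AEs over the duration of treatment will be provided for each treatment group". That phrase can be read as shorthand for the window in 3.5.1, because 6.9.1 applies the tiered analysis to treatment-emergent events.

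**Conclusion.** The point holds as a gap in a stated rule. Followed literally, SAP 3.5.1 with Protocol 8.1.4 credits extension-period events to the randomised arm, for up to 27 of 112 days (24%) per rollover subject. If the events are held elsewhere, the lag is seen only in non-rollovers.

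With active extension drug, no gap, constant hazards and 70-90% rollover, the common-event risk difference is about 16-17 points instead of 21, and the rare-event difference about 1.6 instead of 2.0. A 14-day gap roughly halves the overlap. These are illustrations that rest on assumed inputs, not estimates of bias in this trial. The efficacy analyses are not affected.

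**What to change.** - In SAP 3.5.1, end the treatment-emergent window at the earlier of last dose plus 28 days and first dose in B7451015.
- State which study's database holds adverse events that start after rollover.
- Add a supportive adverse event table restricted to first to last dose. Truncation alone leaves no-gap rollovers with about 85 days and others with about 112, so rollover status still affects window length in the main table. The supportive table removes that dependence.
- Keep the supportive table as an addition. Making first-to-last dose the main window would drop post-dose events in early discontinuers, who do have the 4-week follow-up in this study.

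The cost is one extra input, the first B7451015 dose date, and one extra table. No new data collection is needed. Unequal window lengths remain in the main table and should be acknowledged in a footnote.

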3. STUDY DESIGN

This is a randomized, double-blind, placebo-controlled, parallel-group, Phase 3 study to evaluate the efficacy and safety of PF-04965842 monotherapy in subjects aged 12 years and older with moderate to severe AD and a body weight ≥ 40 kg. The treatment duration is 12 weeks. Subjects will be screened within 28 days prior to the first dose of investigational product to confirm that they meet the subject selection criteria for the study. A total of approximately 375 subjects will be enrolled from approximately 75 sites located globally. Adolescent subjects below the age of 18 years old (or country-specific age of majority) will only be enrolled in this study if instructed by the sponsor and approved by the country or regulatory/health authority. If these approvals have not been granted, only subjects aged 18 years (or country-specific age of majority) and older will be enrolled. A study design schematic is presented in Figure 1.

Figure 1. Study Design Schematic

Qualified subjects completing the 12-week treatment period of the study will have the option to enter a long-term extension (LTE) study B7451015. Subjects discontinuing early from treatment, or who are otherwise ineligible for the LTE study will undergo a 4 week follow-up period in B7451012.

Subjects who have chronic moderate to severe AD as defined per the inclusion criteria will be randomized to receive 200 mg or 100 mg PF-04965842 once daily (QD), or matching placebo. Investigators, subjects, and the sponsor study team will be blinded as to treatment group.

After providing informed consent, subjects will be assessed for study eligibility at the screening visit. For subjects younger than 18 years old (or country-specific age of majority), their parent(s)/legal guardian will provide supplementary or sole written consent and minor children will provide assent, according to local regulations and rules regarding ability to give assent and consent. Subjects will undergo screening within 28 days prior to randomization. During the screening period, treatments for AD will be washed out, as applicable, according to eligibility requirements. Subjects may be re-screened once if they fail the screening evaluation for reasons related to incidental transitory conditions, unless the reason for the screen failure the disease severity inclusion criteria.

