- QuantiFERON® – TB Gold test (unless performed within 12 weeks of Day 1). If Mantoux PPD tuberculin skin test is required to be performed instead, per [Section 7.2.4](#), the subject must return between 48-72 hours post-injection for evaluation of induration (see [Section 7.2.4](#) for further details on TB testing);
- Conduct clinical evaluations including IGA, SCORAD, EASI and BSA (calculated in the EASI);
- Assess need for contraception and adherence to applicable lifestyle requirements ([Section 4.4](#)). Establish willingness and ability to comply with lifestyle requirements going forward in the study;
- Review Inclusion and Exclusion criteria for subject eligibility;
- Assess for occurrence of Adverse Events: The adverse event and SAE reporting period starts with the signing of the informed consent document;
- If the subject is eligible for continued participation, provide subject with emergency contact card.

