8.2. Definitions

8.2.1. Adverse Events

An AE is any untoward medical occurrence in a study subject administered a product or medical device; the event need not necessarily have a causal relationship with the treatment or usage. Examples of AEs include, but are not limited to:

- Abnormal test findings;
- Clinically significant signs and symptoms;
- Changes in physical examination findings;
- Hypersensitivity;
- Progression/worsening of underlying disease;
- Drug abuse;
- Drug dependency.

Additionally, AEs may include signs and symptoms resulting from:

- Drug overdose;

- Drug withdrawal;
- Drug misuse;
- Drug interactions;
- Extravasation;
- Exposure during pregnancy (EDP);
- Exposure via breastfeeding;
- Medication error;
- Occupational exposure.

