8.3. Severity Assessment

If required on the AE page of the CRF, the investigator will use the adjectives MILD, MODERATE, or SEVERE to describe the maximum intensity of the AE. For purposes of consistency, these intensity grades are defined as follows:	
MILD	Does not interfere with subject's usual function.
MODERATE	Interferes to some extent with subject's usual function.
SEVERE	Interferes significantly with subject's usual function.

Note the distinction between the severity and the seriousness of an AE. A severe event is not necessarily an SAE. For example, a headache may be severe (interferes significantly with the subject's usual function) but would not be classified as serious unless it met one of the criteria for SAEs, listed above.

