1. VERSION HISTORY

This is the third amendment of the Statistical Analysis Plan (SAP) for Study B7451012 and is based on Amendment 5 of the protocol dated 05JUN2018.

Table 1. Summary of Changes

Version/ Date	Associated Protocol Amendment	Rationale	Specific Changes
1 19 Feb 2018	Amendment 1 03 Nov 2017	N/A	N/A
2 22 Jun 2018	Amendment 3 16 Mar 2018	Clarification or completion of prior version	
Added change from baseline in total EASI score and SCORAD score, respectively as endpoints in Section 3.2.3.
 
Added responder analyses based on PtGA, HADS, DLQI / CDLQI and POEM as endpoints in Section 3.3.1.
 
Updated the definition of TEAE in Section 3.5.1.
 
Added text to include analyses for comparing active dose groups to Sections 5.2.1 through 5.2.4 and Section 6.
 
Removed references to the word “peak” in describing pruritus throughout the document.
 
Added further detail on the Efficacy Assessments and PROs within Appendices 4 and 6 through 8.
 
Additional minor changes to improve clarity and alignment with the protocol.

3 29 Mar 2019	Amendment 5 05 Jun 2018	Blinded data review / Regulatory (FDA) Input	
Replaced jump to reference analysis with a tipping point analysis, which is a more general approach and includes jump to reference as a special case. See sections 5.3.1, 6.1.2, 6.2.2 and Appendix 3.
 
Added an additional analysis option for handling binary missing data in Section 5.3.1. Updated the analysis of the NRS4 endpoint as regards handling of missing data in Sections 6.3.1 and 6.4.1 to account for a technical error in the process of transmission and collection of electronic data with the device that led to the NRS data not being collected across several sites.
 
Added a responder endpoint based on recently published data on the PSAAD in Section 3.3.1.

090177e1912f28b6\Approved\Approved On: 26-Jun-2019 09:22 (GMT)

			
Removed (with justification) from Sections 3.3.1 and 6.5, all references to the endpoint based on frequency of pruritus as based on the NRS.
 
Removed responder analysis based on POEM as an endpoint in Section 3.3.1.
 
Updated the definition of a treatment emergent adverse event (TEAE) in Section 3.5.1, in alignment with the latest CaPS algorithm.
 
Additional minor changes to improve clarity and alignment with the protocol.

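### The TEAE definition goes by onset date alone, so a pre-dose event that worsens or becomes serious on treatment can be missed in the TEAE tables and tiered comparisons

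*SAP*

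**What the plan says.** SAP 3.5.1 makes onset the only test: "An adverse event will be considered a Treatment-Emergent Adverse Event (TEAE) if the event started during the effective duration of treatment". The window opens at first dose and closes before last dose plus a 28-day lag. The section then states: "The algorithm will not consider any events that started prior to the first dose date". No exception follows for a change in severity or seriousness. The SAP version history shows that the rule was a deliberate choice in version 3: "Updated the definition of a treatment emergent adverse event (TEAE) in Section 3.5.1, in alignment with the latest CaPS algorithm".

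The flag feeds the comparative safety analysis. SAP 6.9.1 applies the three-tier approach to treatment-emergent events. SAP 3.5.1 names herpes zoster and serious infections as Tier 1, and SAP 5.2.6 reserves p-values for that tier.

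On collection, Protocol 6.1 says: "The adverse event and SAE reporting period starts with the signing of the informed consent document". Protocol 8.1.4.2 adds: "During the active collection period, both non-serious AEs and SAEs are recorded on the CRF". The pre-dose interval can last 28 days, and Protocol 3 says of it: "During the screening period, treatments for AD will be washed out, as applicable, according to eligibility requirements". Where the CRF asks for severity, Protocol 8.3 uses mild, moderate or severe "to describe the maximum intensity of the AE". Protocol 8.2.1 gives "Progression/worsening of underlying disease" as an example of an AE.

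**The concern.** A treatment-emergent definition should capture what changes on drug. That includes new events and also existing events that get worse. Here the second kind is shut out by the stated rule.

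This matters because Protocol 1.4 names viral reactivation and serious or opportunistic infection among the potential risks. SAP 6.9.1 defines a serious infection by the need for hospital admission or parenteral antimicrobials. That need can arise after dosing although symptoms began before it. Under a single continuing record, the event would keep its pre-dose start. It would then be absent from the Tier-1 risk difference, its confidence interval and its p-value.

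The direction of any distortion is not fixed. Worsening of an infection on an immunomodulating drug would, if missed, tend to flatter the active arms. Worsening of a washout flare might be more common on placebo, and missing it would work the other way.

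**Working it through.** The documents give no figure to reproduce: no count of pre-dose AEs and no rate of worsening. The check is a reading of the provisions side by side.

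1. **Can a pre-dose event be on the CRF and still be running at first dose?** Yes. Collection starts at consent (Protocol 6.1, 8.1.4), and screening precedes first dose by up to 28 days. Nothing closes an event at randomization.

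2. **Does worsening on drug make it a TEAE?** Not under SAP 3.5.1, if the record keeps its start date. Only the start date is tested, and a pre-dose start is ruled out.

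3. **Do the documents require a new record on worsening?** No.
   - Protocol 8.1.1 and 8.1.4.2 cover recording and follow-up until the event resolves or stabilizes, which fits one continuing record.
   - Protocol 8.3 asks for maximum intensity, which also fits one record but does not prove it.
   - Protocol 5.8 mentions worsening events when concomitant medication changes, but gives no recording rule.
   - The CRF and its completion guide are not among the documents.

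4. **Which outputs depend on the flag?** The TEAE tables and the tiered risk differences (SAP 6.9.1). Other outputs carry no stated onset condition:
   - SAEs and AEs leading to discontinuation (SAP 3.5);
   - the serious-infection endpoint (Protocol 9.3, SAP 6.9.1);
   - the ongoing review of all AEs and SAEs (SAP 6.9).

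5. **How far does eligibility limit the infection example?** A good deal. Exclusion 12 removes three groups:
   - systemic infection within 6 months that needed admission or parenteral treatment, or that the investigator judged clinically significant;
   - skin infection needing systemic treatment within 2 weeks of Day 1;
   - superficial skin infection within 1 week of Day 1.

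   Protocol 4.3 requires the criteria to be met at Day 1. What remains is mainly a mild, non-skin infection not judged clinically significant. Washout flares and other ongoing AEs remain exposed too.

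6. **Size.** Let m be the number of subjects in an arm whose pre-dose event worsens or becomes serious within the window and who are not otherwise counted for that term. Let s be the share of those worsenings entered as a new AE. The shortfall is m × (1 − s).
   - If s = 1, it is zero.
   - If s = 0, it is m.
   - The documents give neither m nor s.
   - One subject is 1/150 = 0.7% of an active arm and 1/75 = 1.3% of placebo.
   - Tier-1 counts may be small: Protocol 1.2.4 reports two herpes zoster cases in the Phase 2b study. Tier 2 needs at least 4 subjects in any treatment group, so moving one subject from 3 to 4 would decide whether a term is compared at all.

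**The case against.** The best case against the point has four parts.

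- **The rule is a sponsor standard.** SAP 3.5 defers safety definitions to CaPS, and CaPS may pair the onset rule with a convention that worsening opens a new record. That may be so, but CaPS is not reproduced in either document. Alignment explains where the rule came from; it does not say how on-drug worsening is captured.
- **The protocol treats worsening as an AE.** Protocol 8.2.1 lists progression or worsening of the underlying disease. Protocol 8.2.4 implies that an admission caused by worsening of a pre-existing condition can count as an SAE. This makes new records plausible. It is still not an instruction, and it does not say what start date to use.
- **Serious outcomes remain visible elsewhere.** This stands. SAE, discontinuation and serious-infection summaries are not worded as treatment-emergent, and Protocol 9.6 provides blinded adjudication of opportunistic infections. A reader might infer that a serious infection would vanish from the safety report; the documents do not support that. The exposure is confined to the TEAE tables and tiered comparisons.
- **Eligibility blocks most infection examples.** This largely stands, and it narrows the point without removing it.

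Two other stronger readings should be resisted. A reader might infer that events arising in washout are undercounted. They precede randomization and first dose, so leaving them out of TEAEs is correct; only their later worsening is at issue. A reader might also infer that the CRF holds a single start date per event, so that worsening is certainly lost. Neither document says so.

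**Conclusion.** The point holds in a limited form. SAP 3.5.1 has no provision for a pre-dose event that increases in severity or becomes serious on treatment. Unless sites enter such worsening as a new AE, it is missed in the TEAE tables and in the Tier-1 and Tier-2 risk differences.

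The conclusion rests on the wording of the SAP and on the silence of both documents about recording worsening. It does not rest on any evidence that events have been missed. The undercount has no derivable size and may be zero, and its direction between arms is unknown. No efficacy result or error rate is affected. It is worth correcting because the tiered comparison is where the plan sets its safety risks formally against placebo, and Tier-1 events may be few.

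**What to change.** Make two linked changes.

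- **SAP 3.5.1:** also flag as a TEAE any event with onset before first dose that increases in severity or becomes serious on or after first dose and before last dose plus 28 days.
- **CRF completion note:** have sites enter such worsening as a new AE with its own start date. This supplies the date that the extended flag needs.

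A listing of pre-dose AEs that continue on treatment would let a reader check the result. SAP version 3 already cites a blinded data review, so some records may predate the note. Those would need a query to sites before unblinding.

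The cost is a small programming exception to the sponsor standard, the CRF note and possibly slightly higher TEAE counts. SAP 5.2.6 counts subjects, not episodes, so a subject with both an old and a new record for the same term is counted once. If sites already enter worsening as a new AE, the change alters no counts and only makes the convention explicit.
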